#### **Notes:**

- \_IMPUTATION\_ variable represents an ID variable 1 to 100 representing the 100 imputed datasets from the step above.
- The macro variable &i\_act10 and &i\_act25. will contain the delta shift for actual treatment (25mg or 10mg) and &i\_pbo10 and &i\_pbo25. will contain the delta shift for the placebo treatment. The range of delta will be -3\*X to +3\*X by 0.01 litre increments, where X=observed treatment effect difference in litres (active placebo) at Week 52 for the main model analysis. In order to obtain a range of delta symmetrical around 0, X will be rounded to 2 decimal places prior to multiplication. For example, if the treatment difference (25mg placebo) in FEV1 at Week 52 = 0.01 litres, the following table of deltas will be used in order to calculate the p-values corresponding to the grey shaded boxes. A delta of 0ml corresponds to no delta increment/decrement.

Table 20: Secondary Endpoint - Change from Baseline (FEV1): Tipping Point Analysis - Delta Increment / Decrement

				Brensocatib 25 mg – Placebo = $10 \text{ ml } (0.01 \text{ litres}) = x$					
						Active De	elta		
			-30 ml	-20 ml	-10 ml	0 ml	+10 ml	+20 ml	+30 ml
			-3*x	-2*x	-1*x	0	+1*x	+2*x	+3*x
	-30 ml	-3*x							
Delta	-20 ml	-2*x							
De	-10 ml	-1*x							
	0 ml	0*x							
Placebo	+10 ml	+1*x							
Pl	+20 ml	+2*x							
	+30 ml	+3*x							

CONFIDENTIAL Page 129 of 139

### Step 4: Transform the i nomiss dataset to have 1 row per participant per visit and the following variables (i mod1)

_imputation_	Imputation number from 1 to xx representing the xx imputed datasets in the steps above
usubjid	participants identifier
-	
trtn	participants treatment (1=active 25mg, 2=active 10mg,
	3=placebo)
Region1	stratification factor: region1 (With North America as
	reference category)
psaecol	stratification factor: sputum sample for Pseudomonas
	aeruginosa at Screening Visit (positive or negative as the
	reference)
numpes	Stratification factor: number of prior PEs in the previous
	12 months ( $<3$ , $\ge$ 3 as the reference)
agegr3	age group: adult, adolescent (With Adult as the reference)
baseline	Baseline post-bronchodilator FEV1
aval	Post-bronchodilator FEV1 at AVISITN as per the xx imputed
	datasets
chg	Change from baseline for post-bronchodilator FEV1 at
	AVISITN (calculated as AVAL-Baseline)
avisit	Visit identifier corresponding to the change from baseline
	result (1=Wk16, 2=Wk28, 3=Wk40, 4=Wk52)
	•

### Step 5: Fit a MMRM, storing output for each of the 100 imputed datasets corresponding to each fitted delta combination.

```
PROC MIXED DATA=i mod1 METHOD=REML ORDER=DATA EMPIRICAL;
 BY imputation;
 CLASS usubjid trt01pn(ref="3") visit region1(ref="North America")
numpes(ref=">=3") psaecol(ref="Negative") agegr3(ref="Adult");
 MODEL chg = trt01pn avisit trt01pn*avisit region1 numpes psaecol agegr3
baseline / SOLUTION;
 REPEATED visit / SUBJECT=usubjid TYPE=CS RCORR;
 LSMESTIMATE trt01pn
   'Brensocatib 10mg QD vs Placebo: Overall' 1 0 -1,
   'Brensocatib 25mg QD vs Placebo: Overall' 0 1 -1 / CL OM ALPHA=0.05;
 LSMESTIMATE trt01pn*visit
   'Brensocatib 10mg QD vs Placebo: Week 16' 1 0 0 0 0 0 0 0 -1 0 0 0,
   'Brensocatib 10mg QD vs Placebo: Week 28' 0 1 0 0 0 0 0 0 -1 0 0,
   'Brensocatib 10mg QD vs Placebo: Week 40' 0 0 1 0 0 0 0 0 0 -1 0,
   'Brensocatib 10mg QD vs Placebo: Week 52' 0 0 0 1 0 0 0 0 0 0 -1,
   'Brensocatib 25mg QD vs Placebo: Week 16' 0 0 0 0 1 0 0 0 -1 0 0 0,
   'Brensocatib 25mg QD vs Placebo: Week 28' 0 0 0 0 0 1 0 0 0 -1 0 0,
   'Brensocatib 25mg QD vs Placebo: Week 40' 0 0 0 0 0 1 0 0 0 -1 0,
   'Brensocatib 25mg QD vs Placebo: Week 52' 0 0 0 0 0 0 1 0 0 0 -1
/ CL OM ALPHA=0.05;
 ODS OUTPUT LSMEANS = 101sm
             LSMESTIMATES = 11est;
RUN;
```

CONFIDENTIAL Page 130 of 139

NOTE: the 11est dataset will be used to store the mean difference (estimate) and standard error (stderr) for the comparison between active and placebo at Week 52 for each delta adjustment dataset for the 100 imputed datasets.

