#### 8.3.2. Responder Status for Exacerbation-Free over the 52-Week Treatment Period

#### 8.3.2.1. Main Analyses

The Estimand of the responder status for exacerbation-free over the 52-week treatment period is the On-Study Estimand in which all observed data will be included in the analysis (see Section 2). The ITT Analysis Set (see Section 5.2) will be used for this Estimand. The derivation of the endpoint is detailed in Section 6.7.2.

The number and percentage of Responders/Non-responders over the 52-Week Treatment Period will be presented by treatment group.

Responder status at Week 52 will be compared between treatment groups brensocatib vs. placebo using a logistic regression model including treatment group, sputum sample being classified as positive or negative for *Pseudomonas aeruginosa* at Screening Visit, the number of prior PEs [<3 or ≥3] in the previous 12 months, stratification region (North America, Europe, Japan, and the Rest of the World), and age group (adult, adolescent) as fixed effects. If the age group covariate creates estimability issues, it may be removed. An estimate of the odds ratio for the treatment comparison (brensocatib 10mg vs. placebo; brensocatib 25mg vs. placebo) and the 95% Wald confidence interval will be summarized; the corresponding p-value from the Wald chi-square test will be compared to the appropriate alpha level per the multiple test procedure.

For participants who discontinue the study prior to Week 52 without having experienced a PE confirmed through adjudication, their responder status will be missing. To address this issue, first event times for these participants will be imputed based on the observed data model for the time period after discontinuation from the trial. If the imputed event time occurs prior to Week 52, the participant will be considered a non-responder. Otherwise, the participant will be considered a responder. The process of imputing missing PE data will be repeated multiple times to create 100 separate datasets. With each increment, the 100 complete data sets will each be analyzed using the logistic regression model described above. The analysis results will then be combined using Rubin's rules (Rubin 1987).

Technical details for the implementation in SAS can be found in Appendix I.

CONFIDENTIAL Page 59 of 139

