The adjusted means in each treatment group, the adjusted mean differences between treatments, and their 95% Cis at Week 52 will be presented. The p-value for the adjusted mean difference will be compared to the appropriate alpha level per the multiple test procedure.

A figure displaying the adjusted mean changes from baseline over time by treatment group will be provided.

CONFIDENTIAL Page 60 of 139

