### Covariate-adjusted Cox proportional hazards regression model:

#### RUN;

#### Where:

```
trtp participants treatment (1=brensocatib 25mg, 2=brensocatib 10mg, 3=placebo)

region1 stratification factor: region1

psaecol stratification factor: sputum sample being classified as positive or negative for Pseudomonas aeruginosa at screening visit

numpes stratification factor: number of prior Pes [<3 or ≥3] in the previous 12 months

ttpe time to the first PE event (in weeks)

agegr3 adult, adolescent
```

Sorting: data will be sorted by region1, psaecol, numpes, agegr3, ttpe, and usubjid

CONFIDENTIAL Page 117 of 139

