# Secondary Endpoint: Change from baseline in Post-bronchodilator FEV1 at Week 52 – MAIN ANALYSIS

The SAS-Code is the same as defined below in Step 5, except that the main analysis will have no BY-Statement.

Please make sure that records for missing post-randomization visits of participants included in the analysis are artificially created. In the added records the value of the response variable will be missing, but the full information on covariates must be included. This is to create a full correlation structure per participant among (expected) study visits. Refer to below example for visualization with visit 3 to 6 expected:

Dataset as per recorded data: Participants 2 and 3 with missing visits

Participant	Treatment	Covariate	Baseline	Visit	Change from baseline
1	Brensocatib 10mg QD	X	X	3	X
1	Brensocatib 10mg QD	X	X	4	X
1	Brensocatib 10mg QD	X	X	5	X
1	Brensocatib 10mg QD	X	X	6	X
2	Placebo	X	X	3	X
3	Brensocatib 25mg QD	X	X	3	X
3	Brensocatib 25mg QD	X	X	6	X

Dataset with added records for missing visits (italic) but full information on covariates:

Participant	Treatment	Covariate	Baseline	Visit	Change from baseline
1	Brensocatib 10mg QD	X	X	3	X
1	Brensocatib 10mg QD	X	X	4	X
1	Brensocatib 10mg QD	X	X	5	X
1	Brensocatib 10mg QD	X	X	6	X
2	Placebo	X	X	3	X
2	Placebo	X	X	4	•
2	Placebo	X	X	5	
2	Placebo	X	X	6	•
3	Brensocatib 25mg QD	X	X	3	X
3	Brensocatib 25mg QD	X	X	4	•
3	Brensocatib 25mg QD	X	X	5	
3	Brensocatib 25mg QD	X	X	6	X

CONFIDENTIAL Page 127 of 139

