# Random coefficients regression model for Rate of Change in Prebronchodilator and Postbronchodilator $FEV_1$ Over the 52-Week Treatment Period

```
PROC MIXED DATA=... METHOD=REML;
CLASS trtp subject;
MODEL FEV1=trtp time trtp*time / S OUTP=prediction DDFM=KR;
RANDOM intercept time / TYPE=UN SUB=SUBJECT;
ESTIMATE "Regr. coeff. Brensocatib 10mg QD" time 1 time*trtp 1 0 0/CL;
ESTIMATE "Regr. coeff. Brensocatib 25mg QD" time 1 time*trtp 0 1 0/CL;
ESTIMATE "Regr. coeff. Placebo QD" time 1 time*trtp 0 0 1/CL;
RUN;
```

CONFIDENTIAL Page 133 of 139

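### The Appendix I code for FEV1 and responder status contradicts itself on the treatment variable (and, for FEV1, on dose order), so as printed it cannot deliver the dose-versus-placebo tests that the SAP body requires

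*SAP*

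**What the plan says.** **Comparisons required.** SAP Table 3 (Section 6.3.1) gives each endpoint two null hypotheses, one per dose against placebo. H5 and H6 are responder status and H7 and H8 are FEV1, with 25 mg first in each pair. Section 8.3.2.1 asks for "An estimate of the odds ratio for the treatment comparison (brensocatib 10mg vs. placebo; brensocatib 25mg vs. placebo". Section 8.3.3.1 says "The adjusted means in each treatment group, the adjusted mean differences between treatments, and their 95% Cis at Week 52 will be presented", and sends the p-value to the multiple testing procedure.

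**FEV1 code (Appendix I).** Step 4 defines `trtn` as "participants treatment (1=active 25mg, 2=active 10mg", with placebo as 3. Step 1 agrees, and the Cox model for time to first PE has the same order: "trtp participants treatment (1=brensocatib 25mg, 2=brensocatib 10mg, 3=placebo". Step 5 labels its contrasts the other way round: "Brensocatib 10mg QD vs Placebo: Week 52' 0 0 0 1 0 0 0 0 0 0 -1". Its model line is "MODEL chg = trt01pn avisit trt01pn*avisit region1 numpes psaecol agegr3". The main-analysis entry adopts this code: "The SAS-Code is the same as defined below in Step 5, except that the main analysis will have no BY-Statement".

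**Responder code (Appendix I).** The stand-alone logistic block has `trtn` in CLASS and `trtp` in MODEL. It also requests pairwise odds ratios for `trtp`. In the imputation sequence, Step 1 lists `trtp` twice and never `trtn`, Step 3 merges on `trtn`, Step 4 has `trtp` in CLASS and `trtn` in MODEL, and Step 5, described as skeleton code, pools `trtp`.

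**Primary endpoint code.** Section 8.2.1 calls it an example. CLASS and MODEL use `trtp`, but the ESTIMATE statements name `trt`.

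**The concern.** The body names the right comparisons but gives no level coding. A programmer has to take that from Appendix I, which gives two dose orders for FEV1 and does not say which holds.

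Testing is dose-specific: the 25 mg chain runs H1, H3, H5, H7 and the 10 mg chain H2, H4, H6, H8. Exchanged FEV1 labels would credit the Week 52 result to the wrong dose, and the error would carry into the later families of each chain. For responder status, the pooled quantity might not be a log odds ratio against placebo at all.

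Section 1 of the SAP says the analyses are fixed before database lock and unblinding. Settling dose order or parameterization after unblinding would weaken that claim.

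**Working it through.** The plan states no figure on this point, so there is none to reproduce. The check sets the code against its own variable lists and then works out what follows.

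**1. FEV1 dose order**

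| Level position | Stated coding (Steps 1 and 4) | Step 5 label with weight there |
|---|---|---|
| 1 | 25 mg | 10 mg |
| 2 | 10 mg | 25 mg |
| 3 | placebo | placebo (subtracted) |

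The overall contrast labelled 10 mg has coefficients 1, 0, −1. Under the stated coding this is 25 mg minus placebo. The Week 52 row behaves the same way. There are 3 arms × 4 visits = 12 cells, and position 4 is the first arm at Week 52. That is 25 mg under the stated coding and 10 mg only if the levels run 10 mg, 25 mg, placebo.

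The appendix does not settle which order applies. Step 5 uses `trt01pn`, which is not in the Step 4 list. It also sets ORDER=DATA, which makes level order depend on the file, and no sort is stated for this dataset.

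**2. FEV1 visit variable.** Step 4 defines `avisit`. In Step 5, CLASS, REPEATED and the visit-specific contrasts use `visit`, while MODEL uses `avisit`. The contrasts therefore refer to a treatment-by-visit term that the model does not contain.

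**3. Effect of an exchange on the tests.** p7 and p8 would trade places in full. The primary endpoint is nearly protected. In Appendix J, p8 enters the adjusted p-value for H1 only through f(p1, p8) = 2 min(p1/(1+γ1), p8/(1−γ1)), with γ1 = 0.9. This is at most 2p1/1.9 = 1.053 p1. The same bound holds for H2 through p7.

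**4. Responder status with `trtn` outside CLASS.** If `trtn` is numeric (1, 2, 3), Step 4 fits log odds = a + b·`trtn`. The log odds ratio against placebo is then −2b for 25 mg and −b for 10 mg, so OR(25 mg) is forced to equal OR(10 mg) squared. Examples with assumed responder proportions, 540 per arm and no covariates:

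| 25 mg / 10 mg / placebo | True ORs (25 mg, 10 mg) | ORs implied by one slope |
|---|---|---|
| 48 / 48 / 40% | 1.38, 1.38 | 1.38, 1.18 |
| 55 / 40 / 40% | 1.83, 1.00 | 1.84, 1.36 |
| 40 / 55 / 40% | 1.00, 1.83 | 1.00, 1.00 |

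**5. Responder status with names aligned but coding not set.** This is an illustration at the Section 3.2 planning inputs: placebo rate 1.2, rate ratio 0.70 (so 0.84 on each dose), dispersion 1, 540 per arm. Covariates and imputation are ignored.

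- P(no PE) = 1/(1 + rate): 1/2.2 = 0.4545 on placebo and 1/1.84 = 0.5435 on each dose.
- Log odds are −0.182 and 0.174, a difference of 0.357. Variance per arm is 1/(540·p(1−p)), about 0.00747 and 0.00746.
- Reference coding: OR = exp(0.357) = 1.43, SE = √(0.00746 + 0.00747) = 0.122, z = 2.92.
- Effect coding (a software assumption): each coefficient is the deviation from the three-arm average, 0.357/3 = 0.119. OR = 1.13, SE = √((4/9 + 1/9)·0.00746 + (1/9)·0.00747) = 0.0705, z = 1.69.

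The two parameterizations estimate different quantities, and only the first is what Section 8.3.2.1 asks for.

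**The case against.** The best defence is that the body governs and is correct, that the primary code is called an example and the responder pooling code a skeleton, and that most mismatches would probably stop the program rather than mislead quietly. The stand-alone responder block also already requests the pairwise odds ratios. All of that stands, and it limits the point to code specification. It does not remove it. The FEV1 code carries no such caveat and is adopted for the main analysis. Code that fails has to be repaired, and the smallest FEV1 repair (rename the treatment and visit variables to those listed) leaves the labels exchanged if the levels follow the stated coding.

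A reader might infer more than the documents support:

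- **That the labels are certainly swapped, or swapped with a calculable probability.** The coding of `trt01pn` is not given and could differ from `trtn`. The sort by participant is stated for the primary endpoint code, not for this dataset, so it cannot be borrowed to produce a probability.
- **That the Week 52 rows lack a coefficient and so hit the wrong visit.** Some rows print short, but the text was extracted from PDF and a zero may have been lost. The source file should be checked. Nothing here rests on it.
- **That Step 6, which pools by label, carries a swap into the main test.** Step 6 belongs to the tipping-point analysis. The main analysis has no imputations to pool.
- **That the responder test will drop to z = 1.69.** That figure describes a hypothetical partial repair under an assumed software default, not the printed code.
- **That the random-coefficients code proves a conflict**, because it puts 10 mg first: "ESTIMATE 'Regr. coeff. Brensocatib 10mg QD' time 1 time*trtp 1 0 0/CL". It uses `trtp`. If that holds treatment names, ordinary sorting gives 10 mg, 25 mg, placebo, which agrees with its labels.

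**Conclusion.** Wrong as written, as a code specification that should be fixed. No hypothesis, estimand, alpha or stated comparison is wrong.

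For FEV1 the stated coding and the contrast labels give opposite dose orders. If `trt01pn` carries the stated coding and the levels follow it, the H7 and H8 p-values are exchanged in full, while the adjusted primary p-values move by about 5% at most. Both conditions are assumptions.

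For responder status the problem is the treatment variable and the parameterization, not dose order. The printed code does not yield two odds ratios against placebo. Aligning the names is not enough unless reference coding is set or contrasts are pooled.

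The `trt`/`trtp` slip in the primary example code is minor and of the same kind.

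**What to change.** Before database lock, revise Appendix I as follows.

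- **Throughout:** use one treatment variable with one stated coding.
- **FEV1:** use a single visit variable in CLASS, MODEL, REPEATED and the contrasts. Take level-named Week 52 differences from placebo (LSMEANS on treatment-by-visit with DIFF). Alternatively, fix the level order and match each contrast to the stated coding. Check the printed coefficient rows against the source file.
- **Responder status:** use the same variable in CLASS, MODEL and MIANALYZE, with PARAM=REF and placebo as reference. Alternatively, pool the log odds ratios from the ODDSRATIO statement already in the stand-alone block. Define the merge variable in Step 1.
- **Primary endpoint:** change `trt` to `trtp` in the ESTIMATE statements and tie the contrasts to named levels.
- **QoL-B:** its LSMEANS/DIFF structure is a good template, but correct it first. Its treatment definition lists 10 mg twice and never 25 mg, and its MODEL statement misspells `psaecol`.

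The cost is editing and re-checking appendix code. It needs no new data or participants and changes no hypothesis, estimand or alpha.

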### Step 6: combine the estimates using mianalyze

The code below will be run for each delta adjustment dataset combining the 100 imputed datasets.

```
PROC MIANALYZE DATA=11est;
  MODELEFFECTS estimate;
  STDERR stderr;
  BY label;
  ODS OUTPUT PARAMETERESTIMATES=i_output;
RUN;
```

CONFIDENTIAL Page 131 of 139

### Secondary Endpoint: Change from Baseline in QoL-B Respiratory Symptoms Domain Score at Week 52

#### **MAIN ANALYSIS**

```
PROC MIXED DATA=<dataIn> EMPIRICAL;
 CLASS usubjid trtpn(REF='3') region1 numpes psaecol atptn;
 MODEL chg=trtpn region1 numpes pasecol baseline
             atptn trtpn* atptn;
 REPEATED atptn / SUBJECT=usubjid TYPE=CS RCORR;
 LSMEANS trtpn*atptn / OM CL DIFF=ALL ALPHA=<>;
 ODS OUTPUT DIFFS=<dataOut>;
RUN;
usubjid
              participants identifier
              participants treatment (brensocatib 10mg, brensocatib 10mg,
trtpn
              placebo)
              stratification factor: North America, Europe, Japan, and
region1
              the Rest of the World
             stratification factor: sputum sample being classified as
psaecol
             positive or negative for Pseudomonas aeruginosa at
              screening visit
```

numpes stratification factor: number of prior PEs [<3 or ≥3] in

the previous 12 months

baseline Baseline post-bronchodilator FEV1

chg Change from baseline for post-bronchodilator FEV1 at

AVISITN (calculated as AVAL-Baseline)

atptn Visit identifier corresponding to the change from baseline

result; refer to the mapping of visits in Section 6.7.5.2

### Secondary Endpoint: Change from baseline in QoL-B Respiratory Symptoms Domain Score at Week 52 – Tipping Point (Sensitivity Analysis)

The same analysis as described for Change from Baseline in Post-bronchodilator FEV1 (L) at Week 52 will be applied.

The range of delta will be determined in the same way using -3\*X to +3\*X by a suitable increment, where X=observed treatment effect difference (active – placebo) at Week 52 for the main model analysis. The increment will be selected in order to give suitable detail regarding the tipping point. In order to obtain a range of delta symmetrical around 0, X will be rounded to the same decimal places as the incremental parameter precision prior to multiplication.

### **Exploratory assessments**

A graph consisting of the change from baseline in the QoL-B Respiratory Symptoms Domain to Week 52 (CHG) on the horizontal axis and the cumulative percent of participants experiencing up to that change on the vertical axis will be produced to represent the eCDF.

CONFIDENTIAL Page 132 of 139

Participants with missing data will be considered non-responders. See Section 6.7.5.4 and 6.7.5.5.

### **Mean Cumulative Function**

The mean cumulative function will be obtained by PHREG procedure in SAS. Input will be the analysis dataset ADCE. Before calling PHREG, for each participant the time between Pes (event-free time) and the time from last PE until Week 52 needs to be added. This artificial entry will be censored.

An example of the data structure is given below:

Participant	ASTDY	AENDY	CENS	In ADCE	Artificial
1	45	90	0	1	
1	90	122	1		1
1	123	130	0	1	
1	131	319	1		1
1	320	329	0	1	
1	330	364	1		1

```
DATA in1;
  trtpn=1; OUTPUT;
  trtpn=2; OUTPUT;
  trtpn=3; OUTPUT;
RUN;

PROC PHREG DATA=_06cens COVS(AGGREGATE) COVM;
  MODEL (astdy,aendy) * cens(1) = trtpn;
  BASELINE COVARIATES=IN1 OUT=_10phreg CMF=_ALL_ / NOMEAN;
  ID subjid;
RUN;
```

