#### 8.2.1. **Main Analyses**

The Primary Estimand is the On-Study Estimand in which all observed data up to Week 52 will be included in the analysis (see Section 2). The ITT Analysis Set (see Section 5.2) will be used for this Estimand.

The Annualized Rate of PEs will be analyzed using negative binomial regression as implemented in SAS® PROC GENMOD with robust estimate for the covariance matrix. The latter will be achieved by introducing a REPEATED-Statement identifying participant-ID with TYPE=UNSTR^4 for the covariance as unstructured. The model will include treatment group and the randomization stratification factors (sputum sample being classified as positive or negative for *Pseudomonas aeruginosa* at Screening Visit, the number of prior PEs [<3 or ≥3] in the previous 12 months, stratification region [North America, Europe, Japan, and the Rest of the World]), and age group (adult, adolescent) as fixed effects. If the age group covariate creates estimability issues, it may be removed. If the model still does not converge after removing the age group covariate, other handling including using the parametric covariance estimator instead of the robust sandwich covariance estimator may be applied. The time at risk in years (log scale) will be included in the model as an offset variable. The LOG-link function will be used in the model. The OM option will be used to adjust the co-

**CONFIDENTIAL** Page 52 of 139

<sup>4 TYPE=UNSTR option specifies that the covariance matrix of the scores be estimated empirically.

efficients for the LSMEANS to reflect the observed data. An example SAS code can be found in Appendix I.

The annualized Rate of PE for each treatment group, the ratios of PE rates between each brensocatib dose and placebo, and the associated 95% Cis will be estimated from the negative binomial model. In addition, the frequency distribution of participants experiencing 0, 1, 2, 3, and >=4 exacerbations will be provided.

Occurrence of exacerbation events that meet the protocol definition of PE diagnosis based on independent adjudication process will be explored graphically. The below histograms will be produced. Treatment groups will be distinguished by separate bars.

- Count of PEs reported every month in study starting at Day 1 through Week 52. Differentiation of PEs into study month is detailed in Section 6.7.1.7.

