- Mean Cumulative Function of PEs reported starting at Day 1 through Week 52 will be created (see Appendix I for technical details)
- Count of PEs within the categories: "0", "1", "2", and ">=3"

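### The mean cumulative function code leaves out time before the first PE and participants without a PE, dates events at PE end, and fits treatment as a number, so the planned curves would be wrong.

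*SAP*

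**What the plan says.** SAP Section 8.2.1 lists graphical displays of adjudicated PEs, which "will be explored graphically". One is this: "Mean Cumulative Function of PEs reported starting at Day 1 through Week 52 will be created". It refers to Appendix I for the technical details.

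Appendix I, Mean Cumulative Function, gives four instructions that matter here.

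- Source: "Input will be the analysis dataset ADCE". In the worked example the rows flagged as coming from ADCE are all PEs.
- Rows to add: "for each participant the time between Pes (event-free time) and the time from last PE until Week 52 needs to be added". Their status is "This artificial entry will be censored".
- Example: one participant with six rows, (start, stop, CENS): (45, 90, 0), (90, 122, 1), (123, 130, 0), (131, 319, 1), (320, 329, 0), (330, 364, 1).
- Code: "PROC PHREG DATA=_06cens COVS(AGGREGATE) COVM", followed directly by "MODEL (astdy,aendy) * cens(1) = trtpn". There is no CLASS or STRATA statement. Curves are requested at `trtpn` = 1, 2 and 3.

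Other SAP sections use different conventions. Section 6.7.1 (Table 5) starts On-Study time at risk at randomization and removes PE days. Section 6.7.1.7 assigns a PE to a study month by its onset date. The Cox model in Section 8.3.1.1 declares its covariates in a CLASS statement.

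**The concern.** An MCF at time t estimates the mean number of PEs per participant up to t. That requires everyone under observation to be in the denominator from randomization and each event to be placed when it happens. Appendix I departs from this in three ways.

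1. **Risk set.** Only participants who have already had a PE are ever at risk, and only from the onset of that PE.
2. **Event time.** In the interval (start, stop] the event falls at the stop time, which is the end of the PE. Days inside a PE count as time at risk, although the SAP's own definition removes them.
3. **Treatment.** A single numeric coefficient ties the three arms to a log-linear trend in the code value, so the curves cannot show an order of arms that does not follow the codes.

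This is the planned picture of cumulative PE burden by arm for the primary endpoint. As specified it would sit beside modelled rates with which it cannot agree.

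**Working it through.** **The example participant.** The six rows cover 45 + 32 + 7 + 188 + 9 + 34 = 315 of 364 days. The first 45 days are missing, and four single days fall between rows (for example 122 to 123): 45 + 315 + 4 = 364. Days inside PEs that count as at risk: 45 + 7 + 9 = 61. Events fall on Days 90, 130 and 329. The onsets are Days 45, 123 and 320.

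**Scenario.** The inputs are from Protocol Section 10.1: placebo rate 1.2 per year, rate ratio 0.70 (active rate 0.84), dispersion 1, 1620 adults (540 per arm). The planned power confirms the reading of these inputs:

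- V = [(1/1.2 + 1) + (1/0.84 + 1)]/540 = 4.0238/540 = 0.00745, so the SE is 0.0863.
- |ln 0.70|/SE = 0.3567/0.0863 = 4.13. Subtracting 2.81 (two-sided 0.005) gives 1.32, a power of 0.907, which agrees with the stated 90%.

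**Who drops out of the denominator.** With dispersion 1 and a full year at risk, the probability of no PE is 1/(1 + rate): 1/2.2 = 45% on placebo and 1/1.84 = 54% on active. None of these participants has a row.

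**Size.** Gamma-mixed Poisson simulation over 364 days without dropout. The documents give no PE duration, so 14 days is assumed (range 7 to 21). The table shows the Week 52 MCF from one simulated trial with the arms estimated separately, which isolates the effect of the rows.

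| Rows | 25 mg | 10 mg | Placebo | 25 mg/placebo | 10 mg/placebo |
|---|---|---|---|---|---|
| From randomization, event at onset, everyone included | 0.817 | 0.802 | 1.078 | 0.76 | 0.74 |
| Appendix I as written | 4.000 | 4.149 | 4.350 | 0.92 | 0.95 |
| Appendix I plus a censored row 0–364 for participants without a PE | 1.028 | 0.977 | 1.361 | 0.76 | 0.72 |

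The first line equals the observed number of PEs per participant. The second is 4.000/0.817 = 4.9, 4.149/0.802 = 5.2 and 4.350/1.078 = 4.0 times too high. The early part is worse: at Day 28 the specified rows give 0.78, 0.83 and 0.69 against 0.065, 0.050 and 0.072.

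With 7-day PEs the specified rows give 5.09, 4.86 and 5.81 against 0.81, 0.79 and 1.21. With 21-day PEs they give 3.55, 3.47 and 3.94 against 0.77, 0.79 and 1.02.

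Runs averaged over 15 to 30 replicates with 14-day PEs give 3.8 to 3.93 on active and 3.95 to 4.16 on placebo as specified (ratio 0.94 to 0.98). The correct values in those runs are 0.77 to 0.79 and 1.04 to 1.09 (ratio 0.71 to 0.76).

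**Event at PE end, taken alone.** With the time before the first PE restored and everyone included, the Week 52 level is right (0.818, 0.802, 1.082) but the curve is late. Day 28 values are 0.039, 0.030 and 0.032 against 0.065, 0.050 and 0.072.

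**Numeric treatment, taken alone.** The model is Λ_k(t) = Λ_0(t)·exp(βk), so Λ_2 = √(Λ_1·Λ_3) at every t. With correct rows, the fitted values are 0.772, 0.892 and 1.032, and √(0.772 × 1.032) = 0.893. The arm-wise values were 0.817, 0.802 and 1.078.

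Fitting rates 0.84, 0.84 and 1.2 on codes 1, 2 and 3 returns 0.79, 0.95 and 1.15. Two doses that share a true ratio of 0.70 are then drawn at 0.79/1.15 = 0.69 and 0.95/1.15 = 0.83.

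At the Phase 2 rates in Protocol Section 1.2.2.3 (0.96 on 25 mg, 0.80 on 10 mg, 1.25 on placebo), the trend draws 0.83, 0.91 and 1.00 where the arm-wise values are 0.93, 0.70 and 1.10. The order of the doses is reversed.

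The arm labels here use the coding given with the Cox model, "1=brensocatib 25mg, 2=brensocatib 10mg, 3=placebo". The MCF section does not assign arms to the codes.

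**All of Appendix I as written (its rows and numeric treatment).** The same simulated trial gives 3.96, 4.17 and 4.40, with ratios to placebo of 0.90 and 0.95.

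**The case against.** Four points can be made against this.

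- **Scope.** The MCF is a descriptive display. The negative binomial rates and ratios, the p-values, the gatekeeping procedure, the monthly counts and the time-to-first-PE curves are specified separately. This stands, and it limits the point to the figure.
- **Participants without a PE.** The SAP never says they are left out, ADCE is not defined, and the code that builds the PHREG input is not shown. This is true, but none of the row rules applies to such a participant: there is no PE record, no time between PEs and no last PE. The missing time before the first PE is visible in the example itself. A programmer might repair this, and a level near 4 might be caught in a dry run, but the text, example and code all point the other way.
- **Separation.** If participants without a PE are added, the active-to-placebo ratio is nearly right (table, third line). This stands. The level is then still too high: 22% to 27% for that line, and from 17% to about 30% across runs and assumed durations. The distortion from numeric coding also remains.
- **Precision.** PE duration is assumed, and the runs differ in replicates and set-up. The exact inflation is not settled. Its direction and rough size are the same in every run.

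**Conclusion.** The concern holds. The Appendix I specification does not estimate the mean cumulative number of PEs from Day 1 to Week 52, and each of the three defects distorts the curves on its own. Read as written, at the planning rates with 14-day PEs, it overstates the Week 52 level roughly four- to five-fold and moves the active-to-placebo ratio from 0.71–0.76 to 0.90–0.98. Most of that comes from the risk set, and it rests on participants without a PE having no row, which is the natural reading. The late event times and the numeric treatment code follow directly from the printed model statement and need no such reading. The simulated values depend on the assumed PE duration (7 to 21 days) and on no dropout, and they do not predict trial results. The primary inference is not affected. The specification should be corrected because the figure displays the primary endpoint by arm.

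**What to change.** Rewrite the data step and the PHREG call in Appendix I.

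- **First interval:** (0, onset of first PE], event, with time 0 at randomization.
- **Later intervals:** (end of PE, onset of next PE], event.
- **Last interval:** (end of last PE, Week 52 or study discontinuation], censored.
- **Participants without a PE:** one row, (0, end of follow-up], censored.
- **Treatment:** put `trtpn` in a STRATA statement with no covariate, so that each arm has its own curve. State which arm each code denotes.

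These rows remove PE days from the risk set, in line with Section 6.7.1. State this, because it puts the curve slightly above the plain mean count per participant (1.07 against 1.03 on placebo and 0.77 against 0.75 on active in a large simulation, about 3% to 4%). If the plain mean count is wanted, keep participants at risk during PEs.

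The cost is a few lines of text and code and an updated example table, with no new data. Make the change before database lock and unblinding, since SAP Section 1 treats analyses not described there and performed after unblinding as post hoc.
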